## 9.9 MANAGEMENT OF IOP AFTER SURGERY

This protocol recommends that no IOP-lowering medications should be administered to subjects after the surgery (0 meds on postop day 1) unless medically warranted. Investigators should use their clinical judgement and best practices in determining when and why IOP-lowering medications should be reintroduced and if a subject requires surgical re-intervention to manage IOP.

In the event of a steroid response (IOP increase), the Investigator should use his/her standard of care to treat an increase in IOP; however, hypotensive medications should be discontinued once the topical steroid has been discontinued within the reasonable timeframe as deemed appropriate by the investigator.

If a pressure rise is observed, a paracentesis may be performed as necessary. If a paracentesis is performed and there is no protocol-defined adverse event, the paracentesis will be documented in the subject's medical record, the applicable visit CRF and the Ocular Procedures log. If, however, the paracentesis is performed in conjunction with an AE, then the AE is recorded as such, and the paracentesis is also recorded on the AE CRF as a treatment for the protocol-defined AE (as well as the other CRFs mentioned above).

Medications which have been re-started by the investigator may be discontinued if the investigator's judgment is that the target intraocular pressure has been reached and the continued use of some or all of the therapy may not be required. Discontinuation of medications after re-introduction is recommended to be in the reverse order of re-

introduction. The rationale for discontinuation should also be documented in the study record by the investigator.

A record of all ocular hypotensive medications added, discontinued or changed will be documented on the appropriate Case Report Form for each scheduled visit or on a Case Report Form for an Unscheduled Visit, if necessary.

Another potential reason for intervention is hypotony. Intervention should only be considered if the hypotony has caused or is likely to cause sequelae such as a flat chamber or retinal detachment. No intervention is indicated when the vision is unchanged from screening, there is no persistent choroidal detachment, the anterior chamber is not flat with lens corneal touch, or the patient is asymptomatic. No intervention should be undertaken for hypotony which is not causing, or threatening to cause, a reduction in vision.

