#### Primary Effectiveness Endpoint

The statistical hypotheses for the primary effectiveness endpoint, proportion of eyes with a  $\geq 20\%$  reduction in unmedicated mean diurnal IOP at the 12-month postoperative examination (P1), are  $H_0: P1 \leq 0.4$  and  $H_a: P1 > 0.4$ . The performance goal of 0.4 is based on Ahmed et al. that 56% of Hydrus pseudophakic eyes had an outcome of 0 medications and 20% IOP reduction and 11% of 2-iStent eyes had the same outcome. The average of these two reported rates of 0 medications with IOP reduction of  $\leq 20\%$ , 33.5%, was used for determining the performance goal of this study. However, the article mentioned that 20% of 2-iStent eyes did not have the terminal hypotensive medications washout. As such, the rate of 11% of the 2 iStent eyes might be an under-estimation of the true rate of unmedicated IOP reduction of  $\leq 20\%$ . Therefore, a performance goal of 40% (the closest integer larger than 33.5%) is used as the performance goal of the primary effectiveness endpoint of the study.

Based on the adjusted normal distribution approach with a one-sided significance level of 0.025 (or two-sided 0.05), a sample size of **91** eyes with evaluable data at 12 months provides a statistical power of 80% at a true  $P1 = 0.55$ .

Only the study results demonstrate that the device is effective based on the primary effectiveness endpoint (i.e. one-sided p-value  $< 0.025$ ), the formal statistical and clinical conclusions for the secondary effectiveness endpoints will be performed. Therefore, the overall two-sided significance level for the secondary effectiveness endpoints will be 0.05.

[REDACTED]

[REDACTED]

---

 Iqbal [name], [name], PhD, [name], et al. A Prospective Randomized Trial Comparing Hydrus and iStent Microinvasive Glaucoma Surgery Implants for Standalone Treatment of Open-Angle Glaucoma, The COMPARE Study. *Ophthalmology*. 2020 Jan;127(1):52-61.

[REDACTED]

[REDACTED]

[REDACTED]

[REDACTED]

[REDACTED]

[REDACTED]

[REDACTED]

[REDACTED]

[REDACTED]

[REDACTED]

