## **11.2 ANALYSIS POPULATIONS**

The intent-to-treat (ITT) analysis population includes all subjects who are enrolled and treated, regardless of whether or not they have a protocol deviation. The per-protocol analysis population (PP) is a subset of ITT, which includes all subjects who have ab-interno transluminal viscoelastic delivery and trabeculotomy, 12 month IOP (or hypotensive medications washed out IOP if the medications can be washed out) and medication data, and have no clinically significant protocol deviations. It should be noted that the ITT subjects with an uneventful study procedure but with SSIs before the 12-month visit will be included in the PP population even if they do not have the 12-month IOP and medication data. The primary analyses on the primary and secondary endpoint analyses will be carried out on the per-protocol population.

The safety data will be summarized based on the ITT population. The primary and secondary endpoint analyses will also be performed on the ITT population.

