### **11.4.1 PRIMARY EFFECTIVENESS ENDPOINT**

Proportion of eyes with a  $\geq 20\%$  decrease in unmedicated mean diurnal IOP at the 12-month postoperative examination compared to baseline will be calculated. The binomial distribution will be used to derive the exact 95% confidence interval of the percent. The

proportion will be compared against the performance goal of 0.4 (or 40%) based on binomial distribution.

[REDACTED]

For the analyses based on the ITT population, the following imputation for subjects with missing 12-month data but without SSI may be performed:

- The within-eye worst IOP (collected after 3 months postoperatively or IOP at baseline for the subjects with no data after postoperative 3 months) for the missing 12-month IOP and worst number of IOP lowering medications (collected after 3 months postoperatively or IOP-lowering medication data at baseline for the subjects with no data after postoperative 3 months) for the missing 12-month number of IOP-lowering medications.
- The worst IOP (collected after 3 months postoperatively or IOP at baseline for the subjects with no data after postoperative 3 months) during the study for the missing 12-month IOP and worst number of IOP-lowering medications (collected after 3 months postoperatively or IOP-lowering medication data at baseline for the subjects with no data after postoperative 3 months) during the study for the missing 12-month number of IOP-lowering medications.
- The mean IOP during the study for the missing 12-month IOP and mean number of IOP-lowering medications during the study for the missing 12-month number of IOP-lowering medications.
- The last-observed-carried-forward approach.

**11.4.2** [REDACTED]

[REDACTED]

[REDACTED]

[REDACTED]

- [REDACTED]

[REDACTED]

[REDACTED]

[REDACTED]

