**11.4.4 OTHER IMPORTANT CLINICAL EFFECTIVENESS OUTCOMES**

The analysis will be based on the PP Population.

For subjects treated with hypotensive medications at Screening Visit, the change in number of hypotensive medications from Screening to 12 Month (before washout if it is needed) will be calculated. For subjects treated with SSIs the change in number of hypotensive medications will be assumed to be 0. The descriptive statistics such as mean, standard deviation, median, minimum, and maximum will be used to summarize the change in number of hypotensive medications used at 12 months from Screening. The 95% confidence interval of the mean change will be calculated based on the t-distribution.

The percent change in unmedicated DIOP from baseline to 12 months will be calculated for each eye in the PP population. For eye treated with SSI, the baseline unmedicated DIOP will be used to impute the 12 month unmedicated IOP (i.e. 0% change). The descriptive statistics such as mean, standard deviation, median, minimum, and maximum will be used to summarize the percent change in unmedicated DIOP at 12 months. The 95% confidence interval of the mean percent change will be calculated based on the t-distribution.

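### The visible ITT imputation rules set no off-medication condition, so an eye lost to follow-up on restarted drops can be scored a responder on an unmedicated endpoint

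*Combined protocol and SAP*

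**What the plan says.** Sections 7.1 and 11.4.1 define the primary endpoint on unmedicated mean diurnal IOP (DIOP), with a month-12 washout where needed.

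For the ITT analysis only, section 11.4.1 lists four imputations that may be used when month-12 data are missing and the eye had no SSI. None is named as the main one.

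- Within-eye worst: "The within-eye worst IOP (collected after 3 months postoperatively or IOP at baseline for the subjects with no data after postoperative 3 months".
- Worst during the study, with the same window and the same fallback to baseline.
- Mean: "The mean IOP during the study for the missing 12-month IOP and mean number of IOP-lowering medications during the study".
- "The last-observed-carried-forward approach", with no variable named.

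The first three also impute a number of IOP-lowering medications. The last two carry no time window.

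Other sections bear on whether the source readings are off drops:

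- Section 9.9 recommends that "no IOP-lowering medications should be administered to subjects after the surgery (0 meds on postop day 1) unless medically warranted", and leaves reintroduction to the investigator's judgement. It also requires medication changes to be recorded for each scheduled or unscheduled visit.
- Section 11.4.4 counts medications "from Screening to 12 Month (before washout if it is needed", so some eyes are expected to be on drops at month 12.
- For SSI eyes, section 11.4.4 says "the baseline unmedicated DIOP will be used to impute the 12 month unmedicated IOP (i.e. 0% change". Here the medication state is written out.
- Appendix A, section 20.1, lists Goldmann IOP and unmedicated diurnal IOP as separate procedures.

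Section 11.2 makes the per-protocol (PP) population the main one. It admits eyes with a month-12 IOP, or "hypotensive medications washed out IOP if the medications can be washed out".

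**The concern.** The endpoint asks what the pressure is without drops. The mean and carried-forward rules fill the gap with IOP in whatever medication state the eye was in when measured. An eye whose pressure rose, was put back on drops, and was then lost before month 12 leaves drug-lowered readings as its latest data. Comparing those with an unmedicated baseline credits the effect of the drops to the device.

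The within-eye worst rule is safer but not immune. If every reading after month 3 was on drops, the worst of them is still drug-lowered. With no reading after month 3 it falls back to baseline, which gives a 0% change and a non-responder.

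Apart from SSI eyes, PP requires month-12 data. The ITT analysis is therefore the visible check on what leaving out eyes without those data does to the result. A check that leans towards the device does that job poorly.

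**Working it through.** **1. The plan's own figure.** Inputs from section 11.1: null rate 0.40, true rate 0.55, one-sided 0.025, power 80%.

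n0 = [(1.960·√(0.40·0.60) + 0.842·√(0.55·0.45)) / 0.15]² = 84.5.

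With continuity correction, n = (n0/4)·[1 + √(1 + 2/(n0·0.15))]² = 91.05, against 91 stated. The figure reproduces.

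Under the exact binomial test of section 11.4.1 with 91 eyes, the smallest passing count is 47, and P(Bin(91, 0.40) ≥ 47) = 0.0161.

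**2. Does "IOP" in the list mean unmedicated DIOP?** It may be shorthand, but the text does not say so. The appendix separates the two measurements, and section 11.4.4 writes the unmedicated condition out where it is meant. The imputed medication count implies that visits on drops are foreseen. No visible rule uses that count to deny responder status.

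**3. One assumed eye.** Unmedicated baseline 24 mmHg; postoperative readings 22 and 21 off drops, then 16 and 16 on drops; month 12 missing; no SSI.

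| Rule | Readings used | Imputed IOP | Fall from 24 | Scored |
|---|---|---|---|---|
| Mean | all four postoperative | (22+21+16+16)/4 = 18.75 | 21.9% | responder |
| Carried forward | last | 16 | 33.3% | responder |
| Within-eye worst | after month 3, if only 16 and 16 | 16 | 33.3% | responder |
| Within-eye worst | after month 3, if 22 falls there | 22 | 8.3% | non-responder |
| Mean | off drops only | 21.5 | 10.4% | non-responder |
| Carried forward | off drops only | 21 | 12.5% | non-responder |

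**4. Effect on the ITT proportion.** Assumed: 91 ITT eyes, true rate 0.40, of which m eyes are imputed from on-drops readings and scored responders with probability q instead of 0.40.

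Chance of passing = P(Bin(91−m, 0.40) + Bin(m, q) ≥ 47).

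| m | q = 0.6 | q = 0.8 | q = 1.0 |
|---|---|---|---|
| 0 | 0.016 | 0.016 | 0.016 |
| 1 | 0.018 | 0.020 | 0.021 |
| 3 | 0.022 | 0.029 | 0.036 |
| 5 | 0.027 | 0.041 | 0.060 |

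The expected responder rate moves by m(q−0.40)/91. At m = 3 that is 0.7, 1.3 and 2.0 percentage points.

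As a check with 101 eyes, the passing count is 51 and the chance at m = 0 is 0.021. At m = 3 it becomes 0.028, 0.036 and 0.044.

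**The case against.** **Redaction.** A redacted block stands between the description of the test and the imputation list. Section 11.4.3 refers to an imputation for SSI eyes on the primary endpoint that visible section 11.4.1 does not contain, so scoring rules probably sit in that block. The washout text in section 9.5 and much of the measurement text in Appendix A are also redacted. A restriction to off-medication readings may exist there. This stands as a limit on certainty. It does not change what the visible bullets say.

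**The medication count.** In the assumed eye the imputed mean count is above 0, and a statistician could score such a record a failure on an unmedicated endpoint. That would be sensible, but no visible rule makes the link, and the carried-forward bullet names no count at all.

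**Fragility of the example.** The mean rule does not say whether baseline is averaged in. If it is, (24+22+21+16+16)/5 = 19.8, a 17.5% fall and a non-responder. This stands for the mean rule. Carrying forward 16 mmHg gives a responder either way.

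**Eyes that cannot be washed out.** A reader might infer that these eyes feed the carried-forward rule. Section 11.2, read naturally, does not support that: an eye with a month-12 IOP and medication data qualifies for PP, so its data are not missing. The route that remains is an eye without month-12 data whose later readings were on drops.

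**Stakes.** The imputations are optional and ITT-only, and no visible text rests a confirmatory claim on them. This stands.

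**Completeness of the remedy.** Being off drops is not the same as being washed out, and a single reading is not a diurnal mean. The first point is built into the fix. The second remains a limit of any imputation from routine visits.

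**Conclusion.** The concern holds for the visible text of section 11.4.1. As written, the mean and carried-forward rules, and the within-eye worst rule when every reading after month 3 is on drops, can score a drug-controlled eye a responder. The bias favours the device and is confined to the supportive ITT analysis.

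It is modest if few eyes are involved: about 0.002 to 0.005 on the chance of passing with one eye, and 0.006 to 0.020 with three. One eye among 91 does not take that chance above 0.025 at any q shown; three do at q of 0.8 or more. These sizes rest on assumed values of m and q and on using 91, the evaluable count, as the ITT size. The documents give none of the three, and q = 1.0 is an upper bound.

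A reader might go further in two ways that the documents do not support. One is to say that the trial's primary test has an inflated error rate; the main PP analysis does not use these imputations. The other is to size the problem from the remark in section 11.1 that "the article mentioned that 20% of 2-iStent eyes did not have the terminal hypotensive medications washout". That concerns another device and shows only that a missed terminal washout can happen.

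**What to change.** Add to section 11.4.1: for the primary endpoint, imputed postoperative IOP uses only readings taken off all IOP-lowering medication, washed out as the protocol defines, and compared with the unmedicated baseline. An eye with no such reading is a non-responder, including one whose imputed medication count is above 0 and that has no off-medication reading. If the redacted text already says this, a cross-reference from the list is enough.

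Separately, reconcile the condition in section 11.2 about whether medications can be washed out with the unmedicated endpoint. State how an eye that cannot be washed out is scored in PP and in ITT.

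The cost is wording only, since medication changes are already recorded under section 9.9. Eyes given drops for a short time stay usable through their off-medication readings. The downside is a slightly lower ITT responder rate and, for some eyes, a source visit earlier than the last one attended.

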### 11.4.3 COVARIATE ANALYSIS

The following variables will be examined for their prognostic value to the primary and secondary effectiveness endpoints using the PP population with the imputation used for the IOP-related SSIs:

- Age group (based on observed quartiles)
- Gender (male and female)
- Race (White and non-White)
- Ethnicity
- Baseline IOP group (based on observed quartiles)
- Screening Number of IOP-lowering medications (0, 1, 2, 3 and 4)  
*Note: the grouping of medication number may be changed based on the observed data.*
- Study site

For the primary effectiveness endpoint and the second secondary effectiveness endpoint, Fisher's test will be performed. For the first secondary effectiveness endpoint, one-way ANOVA with one of the factors listed above will be used to check the possible covariate effects. A p-value of 0.15 will be used for evaluating the possible covariate effects.

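### Does the covariate screen need a trend or linear test for age, baseline IOP and medication count in place of Fisher's test and one-way ANOVA?

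*Combined protocol and SAP*

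**What the plan says.** Section 11.4.3 gives its purpose in one sentence: "The following variables will be examined for their prognostic value to the primary and secondary effectiveness endpoints". Three of the listed covariates are ordered. Age and baseline IOP enter as quartile groups ("Baseline IOP group (based on observed quartiles"), and the screening medication count enters as categories 0 to 4, with a note that "the grouping of medication number may be changed based on the observed data".

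The tests are then named by endpoint. "For the primary effectiveness endpoint and the second secondary effectiveness endpoint, Fisher's test will be performed"; for the first secondary endpoint, "one-way ANOVA with one of the factors listed above will be used to check the possible covariate effects". The threshold is stated separately: "A p-value of 0.15 will be used for evaluating the possible covariate effects". This is looser than the two-sided 0.05 that Section 11.4 sets as its default. The readable text has no trend test, linear contrast or continuous-covariate model, and it states no direction or shape for any covariate.

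The primary analysis in Section 11.4.1 stands apart from the screen: the "proportion will be compared against the performance goal of 0.4 (or 40%) based on binomial distribution".

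**The concern.** Fisher's test on a 4 x 2 table and a one-way ANOVA on four groups give the same p-value if the group labels are shuffled. Age, baseline IOP and medication count have a natural order, and many prognostic effects run steadily up or down. A test that spends its single degree of freedom on that direction is then more powerful at the same level.

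At stake would be a false reassurance. With about 91 eyes, a covariate with a moderate gradient could pass through the screen unflagged and be read as having no prognostic value, when the test was merely insensitive. The remedy looks cheap: a few lines of SAP text and no new data.

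**Working it through.** **Inputs from the plan.** 91 evaluable eyes, performance goal 0.40 and assumed response 0.55 (Section 11.1); four quartile groups, five medication groups, Fisher or ANOVA, threshold 0.15 (Section 11.4.3).

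**Inputs assumed.** The documents give no covariate effect size and no covariate distribution. I take quartiles of 23/23/23/22 and vary the effect.

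**The plan's own figure first.** n = [(1.960·√(0.40·0.60) + 0.842·√(0.55·0.45)) / 0.15]² = 84.5. With the continuity correction, (n/4)·(1 + √(1 + 2/(n·0.15)))² = 91.05, which matches the stated 91. The screen itself carries no stated power.

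**Step 1: a steady gradient.** Simulated chance of a flag at 0.15, binary endpoint, normal covariate, 55% response at its mean:

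| OR per SD | linear term | trend on quartiles | planned Fisher | linear minus Fisher (points) |
|---|---|---|---|---|
| 1.0 | 15.1% | 15.4% | 14.5% | – |
| 1.2 | 29.7% | 27.6% | 21.3% | 8.4 |
| 1.5 | 67.0% | 62.4% | 46.8% | 20.2 |
| 1.8 | 88.2% | 84.6% | 71.0% | 17.2 |
| 2.5 | 99.5% | 98.5% | 95.0% | 4.5 |

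The continuous endpoint behaves alike: at correlation 0.20, a linear term flags 68.1% and ANOVA 48.3%. So the loss under a gradient is real. The lenient threshold offsets much of it: at OR 1.5, Fisher at 0.15 flags 47%, and a linear term at the section's default 0.05 flags 46%.

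**Step 2: other shapes.** Exact enumeration over all tables, threshold 0.15, Cochran-Armitage trend test (asymptotic / exact) on the same quartiles:

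| Responder rates by quartile | Fisher | trend, asymptotic / exact | asymptotic trend minus Fisher (points) |
|---|---|---|---|
| 0.55 throughout | 14.8% | 15.8 / 13.3% | – |
| 0.475 to 0.625, even steps | 27.6% | 36.8 / 33.4% | +9.2 |
| 0.40/0.50/0.60/0.70 | 61.8% | 77.2 / 74.3% | +15.4 |
| 0.40/0.40/0.70/0.70 | 83.9% | 88.4 / 86.5% | +4.5 |
| 0.50/0.50/0.50/0.70 | 45.2% | 44.1 / 40.4% | −1.1 |
| 0.45/0.65/0.65/0.45 | 53.7% | 15.6 / 13.2% | −38.1 |
| 0.70/0.40/0.40/0.70 | 83.9% | 12.8 / 10.5% | −71.1 |

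A linear term on the raw covariate does no better than the trend test away from a gradient. In simulation, when only the lowest quartile differs (0.35/0.62/0.62/0.62), linear, trend and Fisher flag 59%, 63% and 66%. When one middle quartile is low (0.62/0.35/0.62/0.62), linear flags 17% and Fisher 65%. For a smooth U-shape (OR 1.8 per SD of the squared term), linear flags 14% and Fisher 40%.

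Part of the gain in the second table also comes from setting an asymptotic test against an exact one. For the 15-point spread, exact against exact, it shrinks from 36.8 − 27.6 = 9.2 points to 33.4 − 27.6 = 5.8.

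**Step 3: baseline IOP.** Section 11.4.1 defines response as a "decrease in unmedicated mean diurnal IOP at the 12-month postoperative examination compared to baseline will be calculated", so measurement error in the baseline creates an apparent gradient by itself. Assume a baseline mean of 24, SD 3.5, SD of the percent fall 15 points, and no true gradient. At reliability 0.90, the linear term flags 22% and Fisher 19%; at 0.80, 37% and 25%; at 0.70, 53% and 37%. For this covariate, some of the extra sensitivity is sensitivity to an artefact.

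**Step 4: running both tests.** If either test may flag, the null rate per covariate rises from about 15% to between 23% and 25%. Over nine ordered screens (3 covariates × 3 endpoints), about 2.1 null flags are expected, against 1.3 as planned. Adding the 1-df test alongside the planned one is therefore not free.

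**The case for a change.** The best case for a 1-df test is that steady gradients are the most plausible shape for age, disease severity and treatment burden, and that a screen for prognostic value should be tuned to the plausible. The figures for that shape reproduce by simulation and by exact enumeration, and the null level shows that the gain does not come from a looser test. The loss is also marked for medication count: with five groups of assumed sizes 9/27/27/18/10 and rates from 0.40 to 0.70, Fisher flags 41.3% and the trend test 59.3% (58.0% exact). A linear term on the count would also be unaffected by the permitted regrouping.

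What stands is the arithmetic, and one caution in reading the results: a covariate that is not flagged in about 91 eyes has not been shown to be without prognostic value.

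What does not follow is that the plan chose wrongly. The gradient is an assumption brought to the plan from outside. Making the 1-df test the only one judged would commit the screen to that shape and leave other patterns to the eye. Freedom to regroup medication count is ordinary for a category variable whose cells may turn out sparse, in an analysis that carries no claim.

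**Conclusion.** The concern does not hold. An omnibus test is a coherent choice for a screen that looks for any association and names no shape, and it keeps its level (14.8% against a nominal 15% for the quartile Fisher test). The alternative gains up to about 20 points under a steady gradient. It roughly breaks even when only one end quartile differs, and it loses between 26 points (smooth U-shape, 40% against 14%) and 71 points (0.70/0.40/0.40/0.70) in the non-monotone patterns tried. Experienced statisticians would reasonably differ on that trade.

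Little hangs on it. The visible primary test against 40% does not use the screen, the readable text attaches no action to a flag, and neither the sample size nor any visible estimate depends on it. Wording such as an exploratory label or a note on regression to the mean could be added, but its absence is not an error.

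The comparison rests on 91 eyes in the screen and on assumed effect sizes, group sizes and covariate distributions. Sections 11.4.2 and 11.4.5 are redacted, so a regression specified there can be neither confirmed nor excluded; the conclusion does not need one.
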